# 13.3. Audit and Inspection

The Investigator will permit trial-related monitoring, audits, ethical review, and regulatory inspection(s) at their site, providing direct access to source data/documents. The

investigator will comply with these visits and any required follow up. Sites are also requested to notify BCTU of any relevant inspections or local audits.

# 13.4. Notification of Serious Breaches

The sponsor is responsible for notifying the REC of any serious breach of the conditions and principles of GCP in connection with that trial or of the protocol relating to that trial. Sites are therefore requested to notify the Trial Office of any suspected trial-related serious breach of GCP and/or the trial protocol as soon as they become aware of them. Where the Trial Office is investigating whether or not a serious breach has occurred, sites are also requested to co-operate with the Trial Office in providing sufficient information to report the breach to the REC where required and in undertaking any corrective and/or preventive action.

Sites may be suspended from further recruitment in the event of serious and persistent non-compliance with the protocol and/or GCP, and/or poor recruitment.

### 14. END OF TRIAL DEFINITION

The end of trial will be the date of the last data capture including resolution of DCFs. This will allow sufficient time for the completion of protocol procedures, data collection and data cleaning. BCTU will notify the Sponsor and REC within 90 days of the end of the trial. Where the trial has terminated early, BCTU will inform the REC and sponsor within 15 days of the end of trial. BCTU will provide the Sponsor and REC with a summary of the clinical trial report within 12 months of the end of trial.

## 15. STATISTICAL CONSIDERATIONS

# 15.1. Sample size

Sample size has been calculated based on the dual primary outcomes measure of:

- Patient-reported quality of physical function scale recovery (using the EORTC-QLQ-C30) at 30 days after surgery
- Surgical complications (using the CCI) score at 30 days after surgery

For the assessment of the physical function domain of the EORTC-QLQ-C30 using the method of Frison and Pocock for repeated measure design (one Baseline and one Post-Randomisation score), 320 participants in each group (640 in total) will provide 90% power

-----

at the 2.5% significance level (two-sided) to detect a 5 point difference (MCID), assuming a SD of 20, correlation of 0.6 and a 20% attrition rate. [53]

For the assessment of CCI score, previous studies have established that the minimum clinical important difference (MCID) is 5 points [51]. A total sample size of 902 (451 in each arm) will provide 90% power at 2.5% significance level (two-sided) to detect the MCID of 5 points in CCI score, considering that for the usual care mean and standard deviation (SD) at 30 days are 9.4 and 19.0, respectively and a 20% attrition rate. [52]

We will adopt the sample size associated with CCI score as it is considered dominant and requires a larger cohort of participants to detect a significant difference.

# 15.2. Analysis of outcomes

A separate Statistical Analysis Plan (SAP) will be produced and will provide a more comprehensive description of the planned statistical analyses. A brief outline of these analyses is given below.

The primary comparison groups will be composed of those participants randomised to the F4S App and Usual Care versus those randomised to Usual Care alone. All analyses will be based on the modified intention to treat principle, i.e., participants will be analysed in the intervention group to which they were randomised irrespective of adherence to randomised group or other protocol deviations, will only include those who received surgery.

For all outcomes, appropriate summary statistics and differences between groups, e.g. mean differences, will be presented. Where possible intervention effects will be adjusted for the minimisation variables listed in Section 6.2.3, and baseline values (where available). Given the structure of the data, nesting of patients by centre, centre will be included in the model in the primary analysis.

For the dual primary outcomes, differences between groups will be presented alongside 97.5% confidence intervals and p-values from two-sided tests also provided. To maintain an overall 5% Type I error rate, each comparison will be tested at a significance level of 2.5% to account for the increase in the risk of type I error associated with making two key comparisons. Thus, statistical significance will be set to p<0.025 (two sided). All secondary outcomes will be presented with 99% confidence intervals and no p-values.

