# 7.2. F4S App and Usual Care

This will combine the usual care interventions as per section 7.1 and use of the F4S App (for a minimum of 2 weeks prior to surgery) with details described in the following sections.

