#### 7.3.1 Structured Home Exercise Programme

Participants are guided through a series of screens to build their own programme, including a range of strengthening, mobility and cardiovascular exercises. Baseline suggestions on programme level/ intensity are made based on a 'sit to stand test' conducted within the App. Once the programme is built, participants are encouraged to exercise daily to achieve

.....

150 minutes of exercise/week as per pulmonary rehabilitation guidelines [38]. Heart rate is recorded using a wearable sensor provided free of charge to the participants. Once each exercise is completed, the participant inputs their perceived intensity using the BORG perceived exertion scales to the App [40]. This data is used to encourage the participant via personalised messages to increase or decrease intensity at the next session to achieve the target intensity of BORG perceived exertion as per rehabilitation guidelines [38]. Regular data uploads allow health care professionals to view participants' progress, whilst the App allows the participant to request support from the health care professional if required. Only these health care professionals can view the information within the App. They will be able to see alerts from the participant through the admin page. The App app has safety messages to advise participants to seek medical advice when required (in the same way that usual care patients are directed to contact depending on the situation)

Participants are also able to record any other exercise they undertake e.g. swimming, running etc. Whilst the programme is focussed on pre-surgery, exercise can also benefit recovery post-surgery [41], so the participant will be permitted to use the programme after surgery for a period of 6 weeks, but it will be adapted/reset according to participants' post-surgery 'sit to stand test' performance (on postoperative day 1).

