### 9. TRIAL PROCEDURES

## Baseline (at least 2 weeks prior to surgery)

The following procedures and assessments should be performed:

- Medical history
- Informed consent
- Randomisation
- Nutritional assessment including weight and height (PG-SGA SF)
- Physical tests Muscle strength hand grip, ISWT and sit to stand test
- Participant completed questionnaires to include IPAQ-E, EORTC-QLC-C30 & LC29, EQ-5D-5L, HADS, Technology Access Questions

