# 10. ADVERSE EVENT REPORTING

No related harms have been reported in the literature regarding App use to facilitate self-management of diet and exercise. Therefore, there is no reason to anticipate any safety concerns arising as a result of this intervention within F4S-2. Events that would be considered as adverse events (AEs) are being collected as part of the outcome measures data collection up to 30 days post-surgery this will include the following:

- Post-operative complications as per Claviden-Dindo classifications see appendix I
- In-hospital mortality
- 30 day mortality

During follow-up, the systematic collection of self-reported data as part of the clinical outcomes will be conducted, this will take place alongside routine medical note review (at mandated time points: day of discharge and 30 days follow up). This will include participant reported summaries of health care visits including any admissions to accident and emergency. The team will also capture whether there have been any deaths and cause of death. The events listed above (with reference to Appendix I) will be reviewed by the Data Monitoring Committee (DMC) at regular intervals as part of the main data set.

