#### **Analysis**

The trial-based analysis will be conducted on an 'intention to treat' basis. Missing data will be accounted for by using appropriate techniques, such as multiple imputation, depending on the extent and type of missing items. As the distribution of cost is usually skewed by the existence of patients with particularly high costs, the calculated mean per-patient cost will be given alongside confidence intervals obtained through non-parametric bootstrap methods. Incremental analysis will be undertaken to calculate the difference in costs and relevant outcomes of the interventions compared. Results will be presented in the form of incremental cost-effectiveness ratios (ICER), reflecting the additional cost per QALY gained. Where appropriate, the joint distribution of cost and outcomes derived from bootstrap simulations will be depicted on a cost-effectiveness plane and will be plotted as cost-effectiveness acceptability curves (CEACs) which will indicate the probability of F4S-2 intervention being cost-effective across a range of possible values of willingness to pay. Sensitivity analyses will be undertaken to explore the impact of alternative values and assumptions on the obtained results.

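### All analyses are limited to operated participants, yet nothing compares who reaches surgery by arm or specifies collection of non-fatal serious events before it

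*Protocol*

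**What the plan says.** **Analysis set.** Section 15.2 states: "All analyses will be based on the modified intention to treat principle". Participants stay in their randomised group, but the set is cut down to those operated on: "irrespective of adherence to randomised group or other protocol deviations, will only include those who received surgery".

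**Timing.** Section 9 places consent and randomisation at the visit headed "Baseline (at least 2 weeks prior to surgery". Section 7.2 describes "use of the F4S App (for a minimum of 2 weeks prior to surgery". Section 7.3.1 says the programme is focused on the period before surgery, although "the participant will be permitted to use the programme after surgery for a period of 6 weeks". Section 6.3 says that neither clinical teams nor participants can be blinded.

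**Outcomes.** Both primary outcomes in section 8.2.1 are measured 30 days after surgery. Nothing in section 8.2 counts participants who proceed to surgery.

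**Harms.** Section 10 says that events which would count as adverse events "are being collected as part of the outcome measures data collection up to 30 days post-surgery". It lists post-operative complications, in-hospital mortality and 30-day mortality. Note review takes place "at mandated time points: day of discharge and 30 days follow up". Any death and its cause are also to be captured, and Table 4 requires the change-of-status form on death. Table 2 schedules complication assessment at discharge and day 30 only.

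**Economics.** Section 16.1 says: "The trial-based analysis will be conducted on an 'intention to treat' basis".

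**The concern.** Randomisation balances the arms on the day of allocation. An analysis limited to those later operated on keeps that balance only if reaching surgery does not depend on the arm. Here the dependence is plausible. The intervention aims to change fitness before the operation, and the pilot described in section 1.2.5 reports better physical function before surgery. Entry needs only a suspected diagnosis, the footnote to Table 2 foresees cancelled operations, and decisions are made by unblinded teams.

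If F4S brings more frail patients to theatre, the benefit is not counted and their complications raise the F4S mean CCI. If F4S loses more frail patients before theatre, its mean CCI falls and the loss goes unreported. Both primary outcomes are exposed.

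The same gap affects safety. A participant who has a non-fatal serious event before surgery and is then not operated on never reaches the discharge or day-30 review, and is outside every analysis.

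**Working it through.** **1. The plan's own figure reproduces.** Inputs from section 15.1: CCI difference 5, SD 19.0, two-sided alpha 0.025, power 90%, attrition 20%.

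- Per arm: n = 2 × (2.241 + 1.282)² × 19² / 5² ≈ 358.4, rounded up to 359.
- With attrition: 359 / 0.8 = 448.75, rounded up to 449 per arm, 898 in total. The protocol states 902, and the small difference is immaterial.

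This point alleges no arithmetic error. Section 15.1 does not say whether the 20% includes participants who are never operated on.

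**2. What follows from the text.**

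| Question | What the protocol provides |
|---|---|
| Can surgery status depend on arm? | Yes: at least 2 weeks from allocation to surgery, open label |
| Is the proportion operated compared? | No outcome in section 8.2, and section 15.2 excludes the non-operated from all analyses |
| Do the sensitivity analyses bring them back? | No: the imputation and CACE analyses in section 15.2.4 fall under the same rule |
| Are pre-operative deaths captured? | Yes: section 10 and Table 4 |
| Are non-fatal serious events before surgery collected? | No process is stated in section 10 or Table 2 |
| Does participant-reported health care use fill the gap? | Not as written: section 10 ties it to follow-up, and the resource questionnaires fall at 30 days and 6 months after surgery |

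**3. Illustration of size.** The protocol gives no non-operation rate, so the inputs p0, p1 and M below are assumptions. Let p0 and p1 be the proportions not operated under usual care and F4S. Let M be the mean CCI of the extra F4S patients who reach surgery. Everyone else has the stated usual-care mean of 9.4, and F4S has no true effect on CCI.

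- Share of the operated F4S group who are extra: (p0 − p1) / (1 − p1)
- Spurious difference: that share × (M − 9.4)

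With p0 = 10%:

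- p1 = 7%: share 0.03 / 0.93 = 3.2%
- p1 = 5%: share 0.05 / 0.95 = 5.3%

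| p1 | M = 20 | M = 30 | M = 40 |
|---|---|---|---|
| 7% | 0.34 | 0.66 | 0.99 |
| 5% | 0.56 | 1.08 | 1.61 |

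Against the 5-point MCID this runs from 0.34 / 5 = 7% to 1.61 / 5 = 32%. The standard error of the planned comparison is 19 × √(2 / 360.8) = 1.41, where 360.8 = 451 × 0.8. The distortion is therefore about a quarter of a standard error (0.34 / 1.41 = 0.24) to just over one (1.61 / 1.41 = 1.14).

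Swapping the two non-operation rates between arms gives the same sizes with the opposite sign, if 9.4 is taken as the mean for patients operated on under either allocation.

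**4. Sensitivity of the illustration.** Take 90% operated under usual care, a further g operated under F4S, and an excess mean CCI of D in those patients. The difference is then g × D / (0.9 + g).

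- g = 2%, D = 10: 0.02 × 10 / 0.92 = 0.22 points
- g = 10%, D = 30: 0.10 × 30 / 1.00 = 3.0 points

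The answer is driven almost entirely by what is assumed.

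**The case against.** **The operated set suits the endpoints.** CCI measures complications of an operation, and physical function is timed from it. This stands: the operated set can remain primary. What does not follow is extending it to all analyses, because a comparison of who reaches surgery needs no operation to be defined.

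**The SAP may add the missing analyses.** Section 15.2 calls itself an outline. But the restriction on all analyses and the list of harms are fixed in the protocol, and an SAP cannot analyse events that were never collected.

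**Patients are already selected for resection at entry (section 4.1).** This limits the scope for F4S to make patients operable, and the protocol gives no basis for a 3 to 5 percentage-point difference in operation rates. The mechanism remains possible but its size is unsupported.

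**Safety coverage is wider than it first looks.** A reader might infer that pre-operative harm vanishes altogether and that the DMC cannot see it. The documents do not support that. Deaths and causes are captured, section 10 gives an end to collection but no explicit start, and section 18.5 sends safety outcomes to the DMC without limiting them to operated patients. Section 7.3.1 also describes heart-rate recording, data uploads and alerts visible to health professionals. However, App alerts exist in one arm only and section 10 does not name them as a safety source. The gap is confined to non-fatal events before surgery.

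**The economic analysis may follow its own plan.** A reader might infer that costs and clinical effects will come from different people. Section 16.1 does not define its intention-to-treat population, follow-up is timed from surgery, and a separate economics plan is foreseen. What is shown is a mismatch of terms.

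**Conclusion.** The point holds in a limited form. As written, the plan would not show a difference between arms in reaching surgery. It also specifies no collection of non-fatal serious events between randomisation and surgery. Either could matter for a programme focused on that interval in an open-label trial.

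The direction of any bias is not known and its size cannot be derived from the protocol. The 0.3 to 1.6 CCI points rest wholly on assumed non-operation rates (10% versus 5-7%), an assumed mean CCI of 20-40 in the extra patients, and no true effect on CCI. They show that the distortion need not be negligible against a 5-point MCID. They do not show that the trial will be biased, or that it will be biased against F4S.

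**What to change.** 1. **Section 15.2.** Keep the operated set as primary for CCI and 30-day physical function. Exempt from the operated-only rule a comparison by arm, in all randomised participants, of the proportion proceeding to surgery, with reasons for not proceeding.
2. **Sensitivity analysis.** Examine both primary outcomes under differential non-operation, for example by giving the non-operated a range of unfavourable values. Do not use a CCI of 0 alone, which would reward an arm for losing patients before theatre. Assign physical-function values across a stated range, because a participant with no operation has no day 30 at which to impute a score.
3. **Section 10.** Record serious events and unplanned admissions, as well as deaths, from randomisation in both arms, including participants who never reach surgery. Report them by arm to the DMC. The item needs its own trigger: the day-of-surgery assessments miss the non-operated, and the change-of-status form covers changes in participation and death.
4. **Sections 15.2 and 16.1.** Reconcile the two population terms and say who is in the economic analysis.

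Cost: a protocol amendment, a short extra form item and one or two extra tables.

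### The stated adjustment rule, read in the ordinary way, gives the CCI primary no covariates beyond smoking, age, BMI and centre, although baseline ISWT and QLQ-C30 physical function are collected in both arms: a missed gain in precision, not an error

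*Protocol*

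**What the plan says.** Protocol section 15.2 gives a single rule for all outcomes: "Where possible intervention effects will be adjusted for the minimisation variables listed in Section 6.2.3, and baseline values (where available"). It also puts centre in the primary model. Section 6.2.3 lists the minimisation variables as smoking (two levels), age (four bands) and BMI (four bands).

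Section 15.1 makes CCI the outcome that determines recruitment: "We will adopt the sample size associated with CCI score as it is considered dominant". Its calculation is "A total sample size of 902 (451 in each arm) will provide 90% power at 2.5% significance level (two-sided") for a 5-point difference, assuming "for the usual care mean and standard deviation (SD) at 30 days are 9.4 and 19.0, respectively and a 20% attrition rate". For the other primary, QLQ-C30 physical function, the same section credits a baseline correlation of 0.6. CCI receives no covariate credit.

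Section 9 and Table 2 place the CCI assessments at discharge and at 30 days only. The baseline list in section 9 includes "Physical tests Muscle strength hand grip, ISWT and sit to stand test", together with QLQ-C30 and other questionnaires. At baseline only the App instructions are confined to the F4S arm. Randomisation appears in that list ahead of the physical tests and questionnaires.

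**The concern.** The usual meaning of adjusting for baseline values is that each outcome is adjusted for its own pre-randomisation value. Physical function has one and CCI cannot, so for CCI the clause adds nothing. The outcome with less power in hand therefore has the thinner model. At about 361 evaluable per arm, physical function has about 97% power under its stated assumptions and CCI about 90%.

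The trial's premise is that physical preparation before surgery lowers complications, so it is reasonable to expect baseline fitness and function to carry some information about CCI. If they do, including them would narrow the CCI confidence interval with no extra recruitment. It would also guard against chance imbalance in fitness, which the minimisation does not address. At stake is some precision on the outcome that sets the sample size, not the validity of the planned comparison.

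**Working it through.** **Inputs (protocol 15.1):** difference 5 points; SD 19.0; two-sided alpha 0.025; power 90%; attrition 20%; 451 per arm. Normal quantiles are 2.2414 (alpha/2 = 0.0125) and 1.2816 (90% power).

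**Step 1: reproduce the stated figure.** n per arm = 2 × 19.0² × (2.2414 + 1.2816)² / 5² = 722 × 12.411 / 25 = 358.4, so 359. Dividing by 0.8 gives 448.75, so 449 per arm and 898 in total. The t-based version gives 360 per arm, 450 after inflation and 900 in total. The stated 902 is reproduced, with no covariate credit in it.

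**Step 2: power as planned.** Evaluable per arm = 451 × 0.8 = 360.8. Standard error = 19.0 × √(2/360.8) = 1.415. Power = Φ(5/1.415 − 2.2414) = Φ(1.293) = 90.2%.

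**Step 3: the other primary, for comparison.** Residual SD = 20 × √(1 − 0.6²) = 16. This needs 255 per arm, or 319 after inflation, against 320 stated. At 360.8 per arm the standard error is 16 × √(2/360.8) = 1.191, and power = Φ(5/1.191 − 2.2414) = about 97%.

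**Step 4: CCI with added baseline covariates.** Let R² be the share of CCI variance explained by baseline ISWT and physical function beyond smoking, age, BMI and centre, with 19.0 taken as the SD before they are added. The protocol gives no value, so the range is assumed. Residual SD = 19.0 × √(1 − R²). The sample-size equivalent is 1/(1 − R²) − 1.

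| Assumed R² | Residual SD | Power, 5 points | 97.5% CI half-width | Equivalent extra participants | Total N for 90% power |
|---|---|---|---|---|---|
| 0 | 19.00 | 90.2% | 3.17 | 0% | 898 |
| 0.02 | 18.81 | 90.8% | 3.14 | 2% | 880 |
| 0.05 | 18.52 | 91.7% | 3.09 | 5% | 854 |
| 0.10 | 18.02 | 93.1% | 3.01 | 11% | 808 |
| 0.15 | 17.52 | 94.4% | 2.92 | 18% | 764 |

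If the true difference were 4 points, power would be 72.1% at R² = 0 and 77.0% at R² = 0.10.

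**Step 5: cost if the covariates explain nothing.** Two covariates use two degrees of freedom out of about 720 (2 × 361 − 2).

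**The case against.** The strongest reply is that nothing in the plan is wrong. Adjusting for the minimisation variables and centre is sound, the sample size reproduces, and the target power is met. Section 15.2 calls itself a brief outline, and a separate SAP could name further covariates. This stands in so far as the point is an improvement and not a correction. It does not remove the point, because section 15.2 states a rule, and for CCI that rule leaves useful data aside.

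A second reply is that the phrase about baseline values is loose and could cover more than the outcome's own baseline. That is possible. But if other measures are meant, the text does not say which, and the covariates of a primary outcome in an open-label trial are better fixed in advance. Naming them settles either reading.

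A third reply is that the gain may be small. This stands. With a mean of 9.4 and an SD of 19.0, CCI must be strongly right-skewed, and a linear R² may be modest. A reader might infer from the trial's rationale that ISWT and physical function are among the best predictors of CCI. The protocol does not show this. The evidence in section 1.2.1 on exercise is a treatment effect and not a baseline correlation. The patient-level predictor quantified there is underweight, which BMI already covers in part.

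A fourth reply concerns the remedy. ISWT depends on effort and QLQ-C30 is self-reported, the trial is open label, and section 9 lists randomisation before both. Values obtained after allocation is known could bring bias into the CCI model. This stands, and it shapes the fix.

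**Conclusion.** The point holds as a missed gain in precision on the outcome that sets the sample size. It rests on the ordinary reading of the adjustment rule in section 15.2 and on an R² that the documents do not give. For an assumed additional 2% to 15% of variance explained, CCI power rises from about 90.2% to between 90.8% and 94.4%, and the CI half-width falls from 3.17 to between 3.14 and 2.92 points. If the measures explain nothing, almost nothing is lost.

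A reader might infer that the trial is underpowered for CCI or that 902 is wrong. Neither follows: the figure is reproduced and meets its 90% target without covariates. A reader might also infer that age and BMI enter the model as broad bands. The bands in section 6.2.3 define the minimisation, and the protocol does not say in what form these variables enter the model.

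**What to change.** In sections 15.2 and 15.2.1, pre-specify baseline QLQ-C30 physical function and baseline ISWT distance as fixed covariates in the CCI model, alongside the minimisation variables and centre.

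In section 9, state that these two measures are taken before randomisation. Use only values obtained before allocation. Treat missing or later-measured values by mean imputation or a missing indicator, so that no participant is dropped from the primary analysis on this account.

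The cost is a few sentences in the protocol, carried into the SAP, and no new data items. The downside is the need for a missing-value rule. The extent of missing ISWT cannot be judged from the protocol: no completion rate is given, and sections 5.1 and 5.2 allow remote consultation and consent while the test needs a marked walking course. Fixing the order of baseline tests and randomisation may also need some adjustment to site procedures.

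### Testing each dual primary at a fixed 2.5% is valid, but Holm's step-down meets the same 5% family-wise error, is never less powerful, and can add up to about 4 points of CCI power

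*Protocol*

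**What the plan says.** Protocol 15.2 gives the purpose of the multiplicity rule as "To maintain an overall 5% Type I error rate", and the rule itself as "each comparison will be tested at a significance level of 2.5% to account for the increase in the risk of type I error". The next sentence sets the significance threshold for both outcomes at a two-sided p below 0.025. The intervals match: "differences between groups will be presented alongside 97.5% confidence intervals and p-values from two-sided tests also provided".

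Protocol 15.1 sizes both outcomes at the same level. For the CCI, the dominant outcome, 902 participants (451 per arm) "will provide 90% power at 2.5% significance level (two-sided) to detect the MCID of 5 points in CCI score". The inputs are a usual-care "mean and standard deviation (SD) at 30 days are 9.4 and 19.0, respectively and a 20% attrition rate". For physical function it asks for 320 per arm at the same power and level, with a 5-point difference, SD 20, correlation 0.6 with baseline and 20% attrition.

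Section 1.2.4 explains that two primaries were chosen so that an effect on either would be picked up, and section 2 frames the aim as improving function and/or reducing complications. Section 15.2.1 adds a supporting multivariate analysis with family-wise error held at 5%. None of these sections describes a step-down rule or any passing of unused alpha from one outcome to the other.

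**The concern.** The fixed split holds each outcome to 2.5% whatever the other shows. Suppose physical function is clearly positive and the CCI gives p = 0.03. The protocol must call the CCI result non-significant, although a procedure with the same 5% family-wise guarantee would allow the claim.

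This case is relevant here because the trial is sized for the CCI. Physical function is therefore overpowered relative to its own target and, if its planned effect is real, would usually release the second 2.5%. At stake is some power on the outcome that drives the sample size, and on the chance of a claim for both outcomes. The validity of the trial is not at stake.

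**Working it through.** **Inputs** (Protocol 15.1 and 15.2): CCI difference 5, SD 19; physical function difference 5, SD 20, baseline correlation 0.6; two-sided alpha 0.025 each; 451 per arm; attrition 20%. The protocol gives no correlation between the two outcomes, so 0, 0.3 and 0.6 are assumed.

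**1. The plan's own figures reproduce.** Per arm, n = 2(z_alpha + z_power)² SD²/d², with z = 2.2414 (two-sided 2.5%) and 1.2816 (90% power).
- CCI: 2 × (3.523)² × 361/25 = 358.4, so 359. Then 359/0.8 gives 449 per arm, 898 in total. The exact t-test gives 360, then 450 per arm, 900 in total. Stated: 902.
- Physical function: residual SD = 20√(1 − 0.6²) = 16, and 2 × (3.523)² × 256/25 = 254.2, so 255. Then 255/0.8 gives 319 per arm (exact t: 320). Stated: 320.

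**2. Power at 902 randomised.** Evaluable per arm: 451 × 0.8 = 360.8.
- CCI: SE = 19√(2/360.8) = 1.415 and 5/1.415 = 3.535. Power is Φ(3.535 − 2.241) = 90.2% at 2.5%, and Φ(3.535 − 1.960) = 94.2% at 5%.
- Physical function: SE = 16√(2/360.8) = 1.191 and 5/1.191 = 4.197. Power is 97.5% at 2.5% and 98.7% at 5%.

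**3. Holm, independent outcomes.**
- CCI power = 0.902 + (0.942 − 0.902) × 0.975 = 0.941.
- Both significant, fixed split: 0.902 × 0.975 = 0.879.
- Both significant, Holm: both p-values below 0.05, less the case where both lie between 0.025 and 0.05. That is 0.9423 × 0.9874 − 0.0403 × 0.0126 = 0.930.

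**4. Dependence on physical function.** Bivariate-normal simulation of the two test statistics, CCI effect fixed at 5 points. CCI power under the fixed split is 90.2% throughout.

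| True physical-function effect | CCI power under Holm (correlation 0 to 0.6) | Gain in points |
|---|---|---|
| 5 | 93.9-94.2% | +3.7 to +3.9 |
| 4 | 92.7-93.7% | +2.5 to +3.5 |
| 3 | 91.2-92.7% | about +1 to +2.5 |
| 2 | 90.4-91.3% | about +0.2 to +1.2 |
| 0 | 90.3-90.4% | +0.1 to +0.2 |

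No Holm gain can take CCI power above 94.2%, its power at 5%. With both effects at 5 points, power for both outcomes goes from 87.9-89.1% to 93.0-93.4%. Power for at least one is 98.6-99.8% under either rule. It must be identical, because Holm's first step is the fixed-split test applied to the smaller p-value.

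**5. Error rates under Holm.** With both nulls true, family-wise error is 4.5-4.9%. With physical function at 5 points and no CCI effect (correlation 0.3), the CCI false-positive rate is 4.9%, against 2.5% under the fixed split. It cannot exceed 5%, because Holm never rejects an outcome with p above 0.05.

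**The case against.** The strongest objection is that nothing in the plan is wrong. The goal, the 2.5% rule, the 97.5% intervals and the sample size agree with one another, and the planned 90% CCI power is delivered. That stands, and it is why this is an optional improvement. A reader might infer that the fixed split is a mistake, or that the trial is underpowered because of it; the document supports neither.

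A reader might also infer that Holm gives materially more CCI power in general. It does not: the 4-point gain needs physical function to have its full planned effect, and it nearly vanishes if physical function does not respond. Nor does Holm help the purpose stated in section 1.2.4, since the chance of success on at least one outcome is unchanged. Its benefit lies in making a claim on each outcome.

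Two costs are real.
- **Agreement of test and interval.** Under the fixed split, a 97.5% interval excludes zero exactly when p is below 0.025. Under Holm that agreement can fail.
- **Independence of the CCI decision.** The fixed split keeps the CCI at 2.5% regardless of physical function, which participants report knowing their allocation (section 6.3). Under Holm, a physical-function result inflated by open-label reporting would relax the CCI threshold to 5%. The effect is bounded: the CCI false-positive rate still cannot pass 5%, and the false physical-function claim would arise under either rule.

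These costs should be disclosed. They do not outweigh the gain under the 5% family-wise standard that the protocol sets itself.

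**Conclusion.** The point holds as a low-cost improvement to a valid rule. For the stated 5% family-wise target, Holm is never less powerful than the fixed split for either outcome. At the protocol's own effects it adds just under 4 points of CCI power and 4 to 5 points of power for both outcomes.

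The figures rest on the protocol's SDs, effects and attrition, on normally distributed test statistics with no allowance for centre, and on assumed between-outcome correlations of 0 to 0.6. The conditional range for the CCI should be quoted with any headline gain.

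**What to change.** Amend Protocol 15.2, and carry the change into the SAP, before outcome data are seen by arm:
- Replace the fixed 2.5% rule and the p<0.025 sentence with Holm's procedure: test the smaller primary p-value at 2.5% and, only if it is significant, test the other at 5%. Equivalently, compare adjusted p-values with 0.05, where the smaller is doubled and the larger becomes the greater of itself and twice the smaller.
- Keep 97.5% intervals as the reported intervals. State that the Holm-adjusted p-values decide significance, so that an interval including zero beside a significant result is not read as a contradiction.
- Record that the CCI false-positive rate may rise from 2.5% to at most 5% when only physical function truly responds.
- Leave the sample size at 902. The gain is conditional and should not be spent on a smaller trial.

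The cost is a few sentences of text. Recruitment, data collection and visits are unaffected.
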